2. Coronary computed tomography angiography (CCTA)
3. Cardiac cine CT

If a subject has had eGFR measured within the prior 6 weeks and is not on diuretics, ACE inhibitors (angiotensin converting enzyme inhibitors), ARBs (angiotensin receptor blockers), and has had no major change in clinical status, then the eGFR does not need to be rechecked. Otherwise, the eGFR will be measured.

CCTA will be performed during an intravenous iodinated contrast infusion. A test bolus of iodinated contrast (approximately 20 ml) will be used to judge contrast bolus arrival time and optimize image quality. CCTA examination is performed with 60-80 ml iodinated contrast according to Clinical Center guidelines.

4. Radiation and iodine contrast dose

The estimated average radiation dose for the entire cardiac computed protocol will be less than or equal to 2.1 rem per year. Iodinated contrast dose will be in accordance with current CT Clinical Center guidelines.

Medication to facilitate imaging

Beta Blockade

In order to optimize image quality by reducing cardiac motion, participants may receive beta blockade on the day of the scan if the expected heart rate is > 60/min. Participants will have heart rate and blood pressure measured, and will be assessed for contraindications to beta blockade (bradycardia, active wheezing and history of adverse reaction).

Beta blockade will proceed according to NHLBI and CC clinical standards: a net dose of metoprolol 25-200 mg or atenolol 50-100 mg or diltiazem 90-360 mg will be administered orally potentially in divided doses over a period of approximately 1-2 hours titrated to achieve a heart rate less than 60 beats per minute. In addition, metoprolol or diltiazem 5-20 mg intravenously may be administered in divided doses at the judgment of the supervising physician if heart rate is not adequately controlled and the subject appears capable of tolerating the additional medication. Vital signs (blood pressure, Heart rate) will be obtained and documented following metoprolol administration. If at any time the heart rate is <50 bpm and/or the systolic BP is <100, and the subject becomes symptomatic the supervising physician will be notified. All participants who receive beta blockers will be assessed for symptoms of bradycardia, hypotension and orthostasis after scan completion.

Nitrates

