2. ELIGIBILITY ASSESSMENT AND ENROLLMENT

2.1. INCLUSION CRITERIA

- A. Men \geq 40 and \leq 75 years of age; women \geq 40 and \leq 75 years of age
- B. Willing to travel to the NIH for follow-up visits.
- C. Willing to start or modify statin therapy.
- D. Able to understand and sign informed consent.
- E. Serum Creatinine \leq 1.5 mg/dL within 30 days in accordance with the NIH Clinical Center Radiology and Imaging Sciences SOP. (http://intranet.cc.nih.gov/radiology/policies/ct_iv_contrast_sop.html)
- F. Eligible for primary prevention statin therapy
 - 1) Eligible for at least moderate intensity statin according to 2013 ACC/AHA GRCR (i.e., \geq 5% 10 year cardiovascular risk, https://my.americanheart.org/professional/StatementsGuidelines/Prevention-Guidelines_UCM_457698_SubHomePage.jsp) **OR**
 - 2) low ($<5\%$) 10 year cardiovascular risk per 2013 ACC/ AHA and with coronary artery calcium score \geq 300 Agatston units or \geq 75 percentile for age, sex, and ethnicity determined per MESA study (<http://www.mesa-nhlbi.org/calcium/input.aspx>).

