2.2. EXCLUSION CRITERIA

- A. Allergy or prior clinically relevant adverse reaction to Rosuvastatin (does not include minor muscle pain).
- B. High intensity statin treatment for more than 90 days prior to enrollment
- C. LDL \geq 190 mg/ml
- D. Physician-diagnosed heart attack
- E. Physician-diagnosed stroke or TIA
- F. Physician-diagnosed heart failure
- G. Having undergone procedures related to cardiovascular disease (CABG, angioplasty, valve replacement, pacemaker or defibrillator implantation, any surgery on the heart or arteries)

- H. Active treatment for cancer
- I. Prior hypersensitivity reaction to iodinated contrast injection
- J. Known hyperthyroidism.
- K. Acute renal failure, renal transplant, dialysis and renal failure clinically diagnosed.
- L. History of liver transplant or severe liver disease or unexplained elevation of baseline ALT>3x upper limit of normal
- M. Pregnancy and nursing
- N. Mental, neurologic or social condition preventing understanding of the rationale, procedures, risks and potential benefits associated with the trial.
- O. Any other conditions that precludes safety for MRI and/or CT imaging per the researcher's evaluation.
- P. Individuals with hemoglobinopathies or severe asthma.
- Q. Severe renal excretory dysfunction, estimated glomerular filtration (eGFR) rate < 30 mL/min/1.73m² body surface area according to the Modification of Diet in Renal Disease criteria
Glomerular filtration rate will be estimated using the MDRD 2005 revised study formula:
eGFR (mL/min/1.73m²) = 175 x (standardized serum creatinine)-1.154 x (age)-0.203 x 0.742 (if the subject is female) or x 1.212 (if the subject is black)

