The primary known risks of nonionic iodinated contrast as utilized in MDCT angiography are hypersensitivity reactions and contrast induced nephropathy. Mild to moderate adverse events such as nausea, injection site pain or urticaria occur in less than 3 percent of patients. Serious adverse events, such as hypotensive collapse, shock and death are reported in less than 1 in 10,000 patients. These reactions are generally considered idiosyncratic. Contrast induced nephropathy (CIN) is defined by an increase in creatinine more than 1 mg/dL or 50% above baseline. The risk of CIN in patients with normal renal function is considered to be negligible. The inclusion criteria for this study require baseline GFR >45 mL/min/m² as calculated by the MDRD equation to minimize risk of nephropathy. Furthermore, injection of less than 100 ccs of iodinated contrast medium is considered to present minimal risk of CIN.

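### Section 7.5 relies on an inclusion criterion of GFR above 45 that sections 2.1 and 2.2 do not contain; their numeric rules admit women with eGFR of about 34 to 45

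*Combined protocol and SAP*

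**What the plan says.** Section 7.5, under iodinated contrast, calls the nephropathy risk negligible in patients with normal renal function and then gives two grounds for reassurance. The first is eligibility: "The inclusion criteria for this study require baseline GFR >45", calculated by MDRD. The unit is printed as mL/min/m²; I read it as the usual mL/min/1.73 m². The second is volume: "injection of less than 100 ccs of iodinated contrast medium is considered to present minimal risk of CIN".

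The eligibility sections say something different:

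- **2.1 E** caps serum creatinine at "1.5 mg/dL within 30 days in accordance with the NIH Clinical Center Radiology and Imaging Sciences SOP". Section 2.1 has no GFR item.
- **2.2 Q** excludes "Severe renal excretory dysfunction, estimated glomerular filtration (eGFR) rate < 30" mL/min/1.73 m² and prints the MDRD formula.
- **2.2 K** excludes "Acute renal failure, renal transplant, dialysis and renal failure clinically diagnosed".
- **2.2 O** excludes "Any other conditions that precludes safety for MRI and/or CT imaging", at the researcher's judgement.

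The CT imaging section says when eGFR must be rechecked before a scan but gives no value at which contrast is withheld. Appendix A schedules creatinine at every CT visit, again without a cut-off. As a renal limit, 45 appears only in section 7.5.

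**The concern.** Section 7.6 names iodinated contrast among the principal risks to participants. The first protection that 7.5 offers against that risk is attributed to the inclusion criteria, yet it is not there. An IRB or DSMB member reading 7.5 would conclude that nobody with eGFR of 45 or below is enrolled. Staff working from the criteria in 2.1 and 2.2 would find no such number to apply.

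The mismatch would be harmless if the creatinine cap already guaranteed eGFR above 45. MDRD carries a factor of 0.742 for women, so one cap for both sexes allows a lower eGFR in women than in men. The question is whether it falls below 45. Participants have contrast CT four times, at baseline, 12, 24 and 36 months.

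**Working it through.** **Inputs.** Creatinine no higher than 1.5 mg/dL (2.1 E); age 40 to 75 for both sexes (2.1 A); eGFR below 30 excluded (2.2 Q); stated limit 45 (7.5). The formula is the one printed in 2.2 Q:

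eGFR = 175 × Cr^-1.154 × age^-0.203 × 0.742 (female) × 1.212 (Black)

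**Step 1: lowest eGFR the cap allows.** eGFR falls as creatinine and age rise, so set Cr = 1.5. At age 75, for a non-Black man: 1.5^-1.154 = 0.6263, 75^-0.203 = 0.4163, and 175 × 0.6263 × 0.4163 = 45.6. For a non-Black woman: 45.62 × 0.742 = 33.85. The range by group:

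| Group, Cr = 1.5 mg/dL | Age 40 | Age 60 | Age 75 |
|---|---|---|---|
| Non-Black women | 38.5 | 35.4 | 33.9 |
| Black women (both factors) | 46.6 | 42.9 | 41.0 |
| Non-Black men | 51.8 | 47.7 | 45.6 |
| Black men | 62.8 | 57.9 | 55.3 |

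The stated limit of 45 is reproduced for men only. Black women cross it between age 47 (45.1) and age 48 (44.9). Non-Black women at the cap are below it at every eligible age.

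**Step 2: creatinine values that pass 2.1 E but give eGFR of 45 or below.** Solve for creatinine at a limit L:

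Cr = (175 × age^-0.203 × factors / L)^(1/1.154)

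For a non-Black woman aged 60 and L = 45: 60^-0.203 = 0.4356, 175 × 0.4356 × 0.742 = 56.6, 56.6 / 45 = 1.257, and 1.257^(1/1.154) = 1.22.

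| Group | Age 40 | Age 60 | Age 75 |
|---|---|---|---|
| Non-Black women | 1.31–1.50 | 1.22–1.50 | 1.17–1.50 |
| Black women | none | 1.44–1.50 | 1.39–1.50 |
| Men | none | none | none (needs at least 1.518) |

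**Step 3: whether 2.2 Q closes the gap.** With L = 30, the lowest creatinine over all groups is 1.67 mg/dL (non-Black woman aged 75), already above the cap. Applied to the same creatinine value, Q excludes nobody whom 2.1 E has admitted.

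**Step 4: the volume argument.** The CT section states: "CCTA examination is performed with 60-80 ml iodinated contrast according to Clinical Center guidelines". It adds a test bolus of about 20 ml. The total is 60 + 20 = 80 ml to 80 + 20 = 100 ml, against the limit in 7.5 of less than 100.

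**Sensitivity.** The printed formula joins the sex and race factors with the word or. The figures above apply both to Black women. If only 0.742 is applied, their values equal those of non-Black women. If only 1.212 is applied, they equal those of Black men and stay above 45. The result for non-Black women is the same under every reading.

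**The case against.** The strongest reply is that 2.1 E is not a bare creatinine cap. It defers to the Clinical Center radiology SOP, and the CT section ties contrast to Clinical Center guidelines. eGFR is measured before CT unless a value from the previous 6 weeks exists in a stable patient who is not on diuretics, ACE inhibitors or ARBs; presumably it would be acted on. If the SOP holds the 45 limit, 7.5 is loosely worded and no such woman would be scanned. This stands as a limit on what can be claimed: the documents show that 45 is not in the written criteria, not that it is never applied. It does not rescue 7.5, which attributes the limit to the inclusion criteria. Exclusion O is discretionary, and neither K nor the pre-scan check states a threshold.

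Three lesser points also have force:

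- Few women may be affected, and the documents do not show that harm would follow at this contrast volume.
- The volume totals reach 100 ml only at the top of the range and with an approximate bolus, so they show a thin margin rather than a contradiction.
- 2.2 Q is redundant only when both tests use the same sample. 2.1 E accepts a value up to 30 days old and Q sets no window, so a later, worse result could trigger Q. Overlap between safety rules is not itself a defect.

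**Conclusion.** The concern holds. Section 7.5 cites an inclusion criterion that sections 2.1 and 2.2 do not contain, and their numeric rules do not imply it. On those rules the lowest admissible eGFR is 33.9, and women with eGFR of about 34 to 45 are admissible: non-Black women at any eligible age, Black women from about age 48 and only down to about 41. Men are unaffected.

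This rests on the protocol's own MDRD formula, with both factors applied to Black women, and on the criteria as written, since the SOP is not available. The number of women involved cannot be estimated. The primary endpoint, sample size and analysis are untouched. It should be fixed because the risk section relies on a safety threshold that the eligibility text does not apply.

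**What to change.** If the limit is intended, add to 2.1 a criterion of MDRD eGFR above 45 mL/min/1.73 m² for iodinated contrast. Leave 2.2 Q and the gadolinium limit of 30 in section 12 as they are. For non-Black women this lowers the effective creatinine ceiling from 1.5 to about 1.31 mg/dL at age 40 and 1.17 at age 75. Men see no change.

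If it is not intended, correct 7.5 so that it describes the patients the criteria admit (eGFR down to about 34), or states the SOP limit and names the SOP as its source. This option leaves eligibility unchanged.

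Either is a one-sentence amendment. eGFR is already among the screening laboratory tests in 2.3 F, so no procedure is added. The cost of the first option is that some women with eGFR of about 34 to 45 become ineligible, and any already enrolled need a documented decision about their remaining contrast scans.

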7.6. RISKS/BENEFITS ANALYSIS

The principal risks to participants are high intensity statin therapy, exposure to ionizing radiation as part of the coronary CT angiogram and receipt of iodinated contrast. As noted in 7.3, above, large clinical trials have demonstrated low rates of significant adverse events due to statins, few if any of which persist after drug discontinuation. The study population has been specifically selected to be at the lowest risk for

ionizing radiation, and the CT protocol carefully tailored to ensure delivery of the lowest possible dosage necessary to generate diagnostic images.

7.7. CONSENT PROCESS AND DOCUMENTATION

Note: Effective January 21, 2019, a witness to the signature of the written long form research consent at an NIH site (whether initially approved by an IRB before or after January 21, 2019) is no longer a requirement.

Patients asked to participate in PET imaging will be consented separately for their participation in the main protocol and the sub study. Patients asked to participate in the Reproducibility sub study will be consented separately for their participation in the main protocol and the sub study. The investigational nature and objective of this trial, the procedures involved and their possible risk and discomforts, potential benefits, and possible alternative therapies will be explained to participants. The subject will be provided with a copy of the consent with enough time to review it and ask questions prior to the consent process. Participants will be enrolled after eligibility criteria have been determined and a signed informed consent document has been obtained. Consent for NIH employee will not be obtained from individuals in their supervisory chain of command.

The investigators roles are listed on the Study Personnel page, which identify who is authorized to obtain informed consent from the study subjects.

Telephone Consent and or Telehealth platform

Participants may be contacted by telephone, and or Telehealth NIH-approved platform to obtain informed consent for new subjects. For subjects actively participating in the study who may need to be re-consented due to changes to the informed consent or procedures. For instance, when new risk information relevant to a subject's ongoing participation is discovered, notification to the subject may be required (applies to all consent documents). Many subjects may have travelled to the NIH CC previously and a return trip would be inconvenient. The telephone consents will be obtained by those investigators designated as authorized to obtain informed consent on the Study Personnel page. Telehealth procedure will follow the NIH- approved policy. Procedures for obtaining telephone consent are as follows:

- The informed consent document will be sent to the patient either by mail (U.S. Postal Service or Fed-Ex), fax, or e-mail prior to the phone conversation. If mailed, a pre-addressed return envelope may be included.
- A telephone call will be scheduled between the participant and designated investigator to allow time for the participant to thoroughly read over the consent. The protocol will be discussed and explained during the scheduled telephone call and any questions will be answered.
- If the patient agrees to participate, the patient will print, sign and date the informed consent document with the date of the telephone conversation.
- The patient is to return the signed document by mail or fax to the investigator. Upon receiving consent, the investigator will print, sign and date the consent with date the telephone conversation occurred and date of receipt of the consent document. This document will be designated as both the original and telephone consent.
- A copy of the fully executed document will be returned to the patient by mail or secure email for the patient's record. The original consent will be sent to medical records to be placed in the patient's electronic chart.

- The informed consent process will be documented on a CRIS progress note (Progress Note – Documentation of Consent) by the investigator.

7.8. DATA SAFETY AND MONITORING

The entire study data set will be managed by the principal investigator. The entire data set will be contained in a secure database located on the NIH server. The forms to record data for this study will be generated and carefully reviewed for completeness, discrepant, inappropriate, and illogical responses. The data will be checked for duplicate entries, with range checks on each field and consistency checks between fields with linked information. In cases of incoherent or missing data, the study coordinator will be immediately contacted and, if necessary, the form returned for CRF correction by the data manager. If multiple problems are found, a larger percentage of patient records will be audited. Non-image study data will be managed through the NICHD Clinical Trials Database system and stored on secure, redundant servers. Study image data will reside on the PACS.

NIH Intramural IRB: Prior to implementation of this study, the protocol and the proposed patient consent forms will be reviewed and approved by the properly constituted IRB operating according to the 45 CFR 46. This committee will also approve all amendments to the protocol or informed consent, and conduct continuing annual review so long as the protocol is open to accrual or follow up of subjects.

A data safety and monitoring board lead by [name]., at the University of Pennsylvania will review all laboratory and safety data. At regular 12-month intervals the DSMB will monitor the safety of the lipid lowering therapy with Rosuvastatin. This will include evaluation of enrollment, compliance, follow-up, laboratory results, data management, and quality control. The DSMB will decide at each of these reviews whether the study will continue as originally designed. Analyses will be conducted for two interim analyses (at the end of year one and year two) and one final evaluation.

Data confidentiality:

Patient image data will be maintained on PACS database systems within the Department of Radiology with security and redundancy at the level of the clinical PACS system used by the NIH clinical center. The confidentiality and security of the data files containing PHI will be maintained by ensuring password protection on all computer accounts. Protection against loss of data is essential to our data management. Copies of the study database files will reside in an independent back-up hard drive.

Data reporting will be done through presenting in national meetings and publishing in journals.

7.9. COMPENSATION

Patients will not receive direct financial compensation for participation in the main study. They will receive the medications Rosuvastatin or Atorvastatin without charge. Participants will be compensated for travel to and from the NIH Clinical Center. For NIH Employees enrolled on this study, refer to NIH Policy Manual, 2300-630-3 – Leave policy for NIH Employees Participating in NIH Medical Research Studies. (See Appendix B)

Reimbursement for the PET and CT reproducibility sub studies will be consistent with NIH guidelines.

For the CT Reproducibility sub study, participants will receive up to \$150 for the visit based on the following:

- Phlebotomy: 1 inconvenience unit
- IV placement: 1 inconvenience unit
- CT with IV contrast: 10 inconvenience units
- Maximum \$30 for visit (\$20 for the first hour and \$10 for each following hour with a maximum of 2 hours per visit)

For the PET sub study, participants will receive up to \$390 total for the 3 additional visits based on the following:

- Phlebotomy: 1 inconvenience unit
- IV placement: 1 inconvenience unit
- PET with IV contrast: 8 inconvenience units
- Maximum \$30 for visit (\$20 for the first hours and \$10 for each following hours with a maximum of 2 hours per visit)

7.10. CONFLICTS OF INTEREST

This study has no external sponsors or funding sources. No investigator has a relevant conflict of interest.

8. SAFETY REPORTING REQUIREMENTS:

8.1. DEFINITIONS

Please refer to Policy 801 for current definitions.

AE assessment:

The NCI Common Terminology Criteria for Adverse Events (CTCAE) version 4.0 will be utilized to describe the severity of AEs.

8.2. IRB REPORTING GUIDELINES

Reports to the IRB and CD:

Expedited Reporting:

Events requiring expedited reporting will be submitted to the IRB per Policy 801 “Reporting Research Events”.

Reports to the IRB at the time of Continuing Review:

The PI or designee will refer to HRPP Policy 801 “Reporting Research Events”, to determine IRB reporting requirements.

Reports to the CD:

The PI or designee will refer to NHLBI DIR guidelines to determine CD reporting requirements.

8.3. IND/IDE:

The magnetic resonance magnets and coils used to perform cardiac imaging are 510k approved devices being used in accordance with their labeling (21 CFR 812 § 812.2(c)). Imaging sequences that are not commercially available (research sequences or works-in-progress) may be used during image acquisition. However, custom tools (software) sequences may be different than what is normally done in a routine clinical scan, these sequences conform to marketed device standards with respect to FDA established safety criteria for static field strength, acoustic noise, dB/dt, RF heating, biocompatibility and performance, all scans done will be performed within FDA safety guidelines. There is no potential for serious risk to the health, safety, or welfare of the subjects using the MRI scanner in these ways. The use of these custom components of the device constitutes a non-significant risk device study. This protocol is therefore eligible for abbreviated IDE requirements of 21 CFR 812.2(b). Consistent with an IDE exempt investigation, any non-commercial imaging sequences will be used solely to address the research questions of this protocol, and not to address the safety or effectiveness of the sequences themselves.

The CT scanners (Somatom Force, Siemens; Toshiba Aquilion ONE) used to perform CT angiography are 510k approved devices and are used in accordance with the labeling (21 CFR 812 § 812.2(c)).

Computed tomography (CT) x-ray imaging has been utilized in the field of medicine for over 3 decades. During this period, introductions of advances in both hardware and software technology have expanded the diagnostic capability of the modality. As CT continues to evolve with even greater capabilities, the potential for providing clinicians with information not currently available today continues to increase.

The Toshiba Aquilion ONE CT system is currently being used for studies in both general CT radiology and CT cardiac imaging. One of the unique aspects of the Aquilion ONE CT system is its ability to acquire whole organ volume images in a single rotation by utilizing an x-ray detector that is configured as 320 detector rows with a 0.5 mm width, providing a z-axis coverage of 16 cm of anatomy. In line with the evolutionary changes to CT systems, the Aquilion ONE will be upgraded with new technology that will expand its capabilities. The changes being made to the Aquilion ONE will provide enhancements to image acquisition capabilities, reduce ionizing radiation dose, and improve subject access to the system. All of these features assist in enhancing the safety of the currently installed Aquilion ONE CT system.

The SOMATOM Force is a whole body X-ray Computed Tomography System which features two continuously rotating tube-detector systems and functions according to the fan beam principle. The SOMATOM Force produces CT images in DICOM format, which can be used by postprocessing applications commercially distributed by Siemens and other vendors. The system software is a command-based program used for patient management, data management, X-ray scan control, image reconstruction, and image archive/evaluation.

